5.6.3.4. Visual field

Visual field examinations will be reported as mean deviation (Humphrey) or mean sensitivity (Octopus) and PSD (Humphrey) or LV (Octopus) in decibels (dB). Visual field mean change from baseline in the study eye will be summarized using descriptive statistics by machine type (Humphrey and Octopus).

CONFIDENTIAL

Draft Statistical Analysis Plan v2.0

XEN-45 Gel Stent

5.6.3.5. Pachymetry

The central corneal thickness in microns will be collected. The mean change from baseline in the study eye will be summarized using descriptive statistics.

CONFIDENTIAL

Draft Statistical Analysis Plan v2.0

XEN-45 Gel Stent

5.7. Other Analyses

5.7.1. Patient Reported Outcomes

Patient Reported Outcomes (PRO) data will be analyzed using ITT population.

5.7.1.1. The SHPC-18 Questionnaire

There will be 7 items on the local eye symptoms and 11 items on the visual function problems as following;

Local Eye Symptoms

- Eye irritation or burning
- Feeling like something is in your eye
- Droopy eyelids
- Excessive tearing
- Skin sensitivity around your eye(s)
- Eye pain
- Red eyes

Visual Function Problems

- Difficulty with distant vision
- Difficulty with near vision
- Changes in depth perception
- Distortion in vision
- Dimming of vision
- Trouble with color vision
- Blurry vision
- Difficulty with light transition
- Difficulty seeing in dark places
- Difficulty with bright lights
- Difficulty seeing when stepping down

Each item will have questions for presence of the symptom, location of the symptom, relativity to glaucoma or its treatment and the severity of the symptoms. A subject listing will be provided for all of the individual items.

The summary of the total bothersome score (sum of all items divided by 18), the summary of the local eye symptom domain bothersome score (sum of all 7 items divided by 7), and visual function problem domain bothersome score (sum of all 11 items divided by 11) will be presented.

CONFIDENTIAL

Draft Statistical Analysis Plan v2.0

XEN-45 Gel Stent

Note that a total score or a domain score will be treated as missing if more than 50% of the corresponding items are missing. In addition, if not all items are answered, then the score will be obtained by taking the average of available items.

See 6.4.1 for detailed analysis instructions.

5.7.1.2. Postsurgical question on resumption of activities and daily routine

The participants will be asked to answer on the question of “Since your glaucoma surgery, would you consider that you have resumed your usual activities and daily routine?”, and the answer choices are “Not at all”, “Somewhat”, “Moderately so”, “Mostly” and “Completely”.

The number and percentage of participants in each category will be presented by treatment group.

5.7.1.3. Work Productivity and Activity Impairment Questionnaire

The following questions will be asked about the ability to work and perform regular activities.

Table 5.7-1 Work Productivity and Activity Impairment Questionnaire

Questions	Answers
Are you currently employed	Yes/No
During the past seven days, how many hours did you miss from work because of your health problems	Number of hours
During the past seven days, how many hours did you miss from work because of any other reason, such as vacation, holidays, time off to participate in this study?	Number of hours
During the past seven days, how many hours did you actually work?	Number of hours
During the past seven days, how much did your health problems affect your productivity while you were working?	Scale of 0 to 10
During past seven days, how much did your health problems affect your ability to do your regular daily activities, other than work at a job?	Scale of 0 to 10

The summary of WPAI:GH in 2 components: percent overall work impairment due to health, and percent activity impairment due to health will be presented for subjects who are currently employed.

A subject listing of all individual elements will be presented.

See 6.4.2 for detailed analysis instructions.

CONFIDENTIAL
XEN-45 Gel Stent

Draft Statistical Analysis Plan v2.0

CONFIDENTIAL

Draft Statistical Analysis Plan v2.0

XEN-45 Gel Stent

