### 17.3 Work Productivity and Activity Impairment Questionnaire

#### Work Productivity and Activity Impairment Questionnaire: General Health V2.0 (WPAI:GH)

The following questions ask about the effect of your health problems on your ability to work and perform regular activities. By health problems we mean any physical or emotional problem or symptom. *Please fill in the blanks or circle a number, as indicated.*

1. Are you currently employed (working for pay)? \_\_\_\_ NO \_\_\_\_ YES  
*If NO, check "NO" and skip to question 6.*

The next questions are about the **past seven days**, not including today.

2. During the past seven days, how many hours did you miss from work because of your health problems? *Include hours you missed on sick days, times you went in late, left early, etc., because of your health problems. Do not include time you missed to participate in this study.*

\_\_\_\_ HOURS

3. During the past seven days, how many hours did you miss from work because of any other reason, such as vacation, holidays, time off to participate in this study?

\_\_\_\_ HOURS

4. During the past seven days, how many hours did you actually work?

\_\_\_\_ HOURS *(If "0", skip to question 6.)*

5. During the past seven days, how much did your health problems affect your productivity while you were working?

*Think about days you were limited in the amount or kind of work you could do, days you accomplished less than you would like, or days you could not do your work as carefully as usual. If health problems affected your work only a little, choose a low number. Choose a high number if health problems affected your work a great deal.*

Consider only how much health problems affected productivity while you were working.

Health problems had no effect on my work	_____	Health problems completely prevented me from working
	0 1 2 3 4 5 6 7 8 9 10	

CIRCLE A NUMBER

6. During the past seven days, how much did your health problems affect your ability to do your regular daily activities, other than work at a job?

*By regular activities, we mean the usual activities you do, such as work around the house, shopping, childcare, exercising, studying, etc. Think about times you were limited in the amount or kind of activities you could do and times you accomplished less than you would like. If health problems affected your activities only a little, choose a low number. Choose a high number if health problems affected your activities a great deal.*

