6.4.2. Work Productivity and Activity Impairment Questionnaire Scoring

WPAI Scoring.pdf

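### The SAP restricts the WPAI activity impairment summary to employed subjects, although the questionnaire also puts that item to subjects who are not employed

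*SAP*

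**What the plan says.** SAP 5.7.1.3 names two WPAI components, overall work impairment and activity impairment, and closes the sentence with a single restriction that covers both: the summary "will be presented for subjects who are currently employed". It adds: "A subject listing of all individual elements will be presented". For detail it points to SAP 6.4.2, where only the name of an attached file is visible: "WPAI Scoring.pdf".

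The questionnaire itself is in Protocol 17.3. Question 1 asks about paid employment, and a subject who has none is told: "If NO, check 'NO' and skip to question 6". Question 6 asks: "how much did your health problems affect your ability to do your regular daily activities, other than work at a job".

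On the population, SAP 5.7.1 states: "Patient Reported Outcomes (PRO) data will be analyzed using ITT population". SAP 5.4 and 5.4.2 agree, and Protocol 11.1.1 also places PRO data in the ITT population. SAP 5.4.2.1, however, assigns PRO to the safety population. None of these sections names an employed subset.

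**The concern.** The employment filter is right for overall work impairment, which needs hours missed, hours worked and productivity at work. It has no evident basis for activity impairment, which the instrument also collects from people without a job. The SAP gives no reason for applying it there. SAP Appendix 2, which records changes from the protocol's analyses, mentions only the sample size reduction.

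Two things are at stake. First, the activity summary would describe a selected part of the trial population. Protocol 8.3.2 admits adults with no upper age limit, so subjects without paid work are eligible, and their question 6 scores would appear in no summary table. Second, the schedules of assessments (Protocol Table 8.1, SAP Table 1-1) place the WPAI at baseline and again after surgery, and question 1 is part of it each time. The SAP does not say which visit determines who counts as currently employed. If it is the visit being summarised, membership is settled after randomisation and may be affected by recovery, so the two groups shown side by side need not be the groups that were randomised.

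**Working it through.** The plan states no figure for this point, so there is none to reproduce. The check sets the questionnaire's routing against the SAP rule, and then illustrates the size.

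**Routing against rule**

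| Subject | Route in Protocol 17.3 | Reaches question 6? | In the SAP 5.7.1.3 activity summary? |
|---|---|---|---|
| Not employed | question 1 to question 6 | yes | no |
| Employed, 0 hours worked | questions 1 to 4, then question 6 ("If '0', skip to question 6") | yes | yes |
| Employed, worked some hours | questions 1 to 6 | yes | yes |

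Every route ends at question 6, but the first row is left out of the summary. The dividing line is paid employment and not hours worked: an employed subject who worked no hours that week stays in.

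**Size, as an illustration**

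Inputs:
- Planned completers: 102, with 68 XEN and 34 trabeculectomy (SAP section 3).
- Employed share f: not in the documents; assumed 30% to 70%.
- Further assumptions: f is the same in both arms, the SD of the score is the same in employed subjects as in all subjects, and every completer answers question 6.

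Formulas:
- Subjects left out = 102 × (1 − f).
- Standard error ratio, employed only against all = 1/√f. This holds for each arm's mean and for the difference.
- 95% interval half-width for a difference in means, in SD units = 1.96 × √(1/n₁ + 1/n₂).

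With all subjects: 1.96 × √(1/68 + 1/34) = 0.41 SD.

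| Assumed f | XEN / trabeculectomy kept | Left out | Half-width (SD) | SE ratio |
|---|---|---|---|---|
| 30% | 20.4 / 10.2 | 71.4 | 0.75 | 1.83 |
| 50% | 34 / 17 | 51 | 0.58 | 1.41 |
| 70% | 47.6 / 23.8 | 30.6 | 0.49 | 1.20 |

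The half-width only gives a sense of scale. The SAP does not clearly plan an interval for this item.

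**The case against.** The best case for the plan has four parts.

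1. *Nothing is lost.* A reader might infer that the answers of subjects without a job are thrown away. The documents do not support that: the answers are collected and appear in the subject listing. They are left out of one summary.

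2. *No comparison is at risk.* A reader might also infer that a planned test between the operations loses power. SAP 5.7.1.3 promises only a summary, and SAP 5.4.2.1 treats secondary endpoints descriptively except those on effectiveness and success. No hypothesis, model or power is stated for the WPAI. The precision loss therefore concerns a descriptive result.

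3. *The focus on workers is partly deliberate, and daily life is covered elsewhere.* Protocol 10.1.1.3 presents the WPAI as a productivity measure. The postsurgical question on resuming activities is summarised by treatment group with no employment filter (SAP 5.7.1.2). The overlap is only partial, because that is one item on return to routine and question 6 rates impairment over the past seven days. A focus on productivity also does not explain why an item about life outside work is limited to workers.

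4. *The scoring attachment may say otherwise.* Its content is not available, and it may define a denominator for each component. That limits what can be said about the plan as a whole. It does not remove the explicit restriction in the SAP text. If the two differ, they need to be reconciled.

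The first two parts stand as limits on the point. The last two soften it but do not answer it.

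**Conclusion.** The point holds. SAP 5.7.1.3 as written applies an employment restriction to activity impairment that fits only overall work impairment, and it gives no reason. Subjects who are not currently employed are directed to question 6, yet they would be absent from its summary. The group that remains may be defined by a status recorded after randomisation.

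The size rests on an assumed employed share of 30% to 70%, with equal SD: about 71 to 31 of 102 completers left out, and a standard error about 1.8 to 1.2 times as large. A higher employed share would make it smaller. A reader might go further and infer that slow recovery removes many subjects from the summary, but the documents do not show this. Question 1 asks about having a paid job, and a subject on leave who worked no hours stays in. How much selection occurs is unknown.

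This is a minor point about a descriptive patient-reported outcome. It does not affect the primary conclusion.

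**What to change.** In SAP 5.7.1.3, split the sentence: present overall work impairment for currently employed subjects, and activity impairment for all subjects in the PRO analysis population who answered question 6, with n by visit and arm. Check that the attached WPAI scoring file agrees. Reconcile SAP 5.4.2.1 (safety population for PRO) with SAP 5.4, 5.4.2 and 5.7.1 (ITT), so that the population is named once.

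The cost is a sentence or two in the SAP and the matching change to the table specifications, which the SAP Introduction says are kept in a separate document. The item is already in the questionnaire, so no new data, visits or eCRF changes are needed. An employed-only activity table can be kept as a supplement if it is wanted.

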5.7.2. Subgroup analyses

There is no subgroup analysis planned in the protocol.

CONFIDENTIAL

Draft Statistical Analysis Plan v2.0

XEN-45 Gel Stent

5.8. Interim Analyses

Even the protocol states that there may be an interim analysis during the study, it is decided that no interim analysis will be conducted for the reason that the study reduced the sample size to 114 from 285 due to the impact of COVID-19 on patient enrollment.

CONFIDENTIAL

Draft Statistical Analysis Plan v2.0

XEN-45 Gel Stent

6. Supporting Documentation

Demographics and baseline characteristics, protocol deviation, and data derivation rules can be found in Appendix 3.

CONFIDENTIAL

Draft Statistical Analysis Plan v2.0

XEN-45 Gel Stent

6.1. Appendix 1 List of Abbreviations

ADE	adverse device effects
AE	adverse event
BCVA	best corrected visual acuity
CI	confidence interval
eCRF	electronic case report form
IOP	intraocular pressure
ITT	intent to treat
LV	
MD	mean deviation
MedDRA	medical dictionary for regulatory activities
mITT	modified intent to treat
PSD	
SADE	serious adverse device effects
SAE	serious adverse event
SAP	statistical analysis plan
SD	standard deviation
SOC	system organ class
TEAE	treatment emergent adverse event
XEN	XEN-45 gel stent

CONFIDENTIAL

Draft Statistical Analysis Plan v2.0

XEN-45 Gel Stent

6.2. Appendix 2: Changes to Protocol-Planned Analyses

A Note-To-File is in place to address the concern of sample size reduction.

CONFIDENTIAL

Draft Statistical Analysis Plan v2.0

XEN-45 Gel Stent

Appendix 3: Supporting Study Information

6.3.1. Demographics

Demographic parameters (age; sex; race) and baseline IOP will be summarized descriptively by treatment group and overall for the ITT population and safety population.

6.3.2. Baseline and Disease Characteristics

The following baseline disease characteristics will be summarized if available:

- Diagnosis: POAG, PXE, Pigment dispersion syndrome, Mixed mechanism glaucoma, uveitic glaucoma, steroid-induced glaucoma, neovascular glaucoma
- Lens status – phakic, pseudophakic, visually significant cataract
- Based on baseline visual field MD, stratification to mild, mod, severe (we can use a published paper as guideline)- see attached
- Medical history: Diabetes, hypertension
- Prior glaucoma procedures – SLT, i-stent, GATT, Kahook Dual Blade (KDB), Endo cyclophotocoagulation (see full list in protocol)

Note that the data were not collected, so there is no corresponding summary table.

6.3.3. Protocol Deviations

Participants reporting major protocol deviations will be summarized in total and by treatment group for the ITT population.

The major protocol deviations that are thought to potentially affect the analysis will be reviewed and finalized in a blinded manner prior to the data base lock. The major deviations are following:

- Prior XEN/trab/tube in study eye
- Prior transscleral ablative procedures in study eye
- No baseline IOP /IOP-lowering medication count recorded
- Wrong study procedure performed
- XEN not implanted (surgery aborted)

6.3.4. Medical and Ophthalmic History

Abnormalities in participants' medical and ophthalmic histories will be coded using the MedDRA.

The number and percentage of participants with abnormalities in medical/ophthalmic history in each SOC and preferred term will be summarized by treatment group and overall for patients in the safety population.

CONFIDENTIAL

Draft Statistical Analysis Plan v2.0

XEN-45 Gel Stent

6.3.5. Prior/Concomitant/Follow-up medications (including dictionary)

Medication data will be coded using World Health Organization Drug Dictionary.

Prior medications include all medications taken prior to day 1 (randomization/treatment visit), whether or not the medication is continuing beyond day 1. Concomitant medications encompass all medicinal products that the participant was taking prior to the day 1 visit that are ongoing at the visit, in addition to all medications that have a start date on or after the day 1 visit date.

Prior and concomitant medication will be tabulated separately for the Safety population. The frequency (number and percentages) of participants who have taken each medication will be tabulated for each treatment group and for overall.

CONFIDENTIAL

Draft Statistical Analysis Plan v2.0

XEN-45 Gel Stent

6.4. Appendix 4: PRO Analysis Instructions

6.4.1. Glaucoma Symptom and Health Problem Checklist (SHPC-18) Scoring recommendations:

Scoring of the
Glaucoma Symptom Checklist

6.4.2. Work Productivity and Activity Impairment Questionnaire Scoring

WPAI Scoring.pdf

6.5. Data handling convention

6.5.1. Analysis Window

Table 6-1 below presents the visits assigned for analyses and the corresponding range of treatment days during which an actual visit may occur.

Table 6-1 Analysis Window

Scheduled Visit	Target Day of the Visit	Analysis Visit Window
Baseline qualifying visit ^a	N/A	N/A
Preoperative Visit 1 ^a	N/A	Up to 28 days before the operation
Visit 2	Day 0	Day of operation
Visit 3	Day 1	6 hours after operation to Day 2
Visit 4	Week 1	Day 3 to Day 10
Visit 5	Week 2	Day 11 to Day 20
Visit 6	Month 1	Day 21 to Day 56
Visit 7	Month 3	Day 57 to Day 119
Visit 8	Month 6	Day 120 to Day 224
Visit 9	Month 9	Day 225 to Day 329

CONFIDENTIAL

Draft Statistical Analysis Plan v2.0

XEN-45 Gel Stent

Visit 10	Month 12	≥ Day 330
----------	----------	-----------

^a Participants may have the baseline qualifying visit and preoperative visit on the same day.

If there are two or more values fall within the same analysis window, the one closest to the target date will be used.

6.5.2. Missing Date Imputation

Dates may be imputed with year, month, and day values under certain scenarios:

Table 6–2 Imputation Scenarios

Scenario	Complete			Imputable
	Year	Month	Day	
1	Yes	Yes	Yes	Complete
2	Yes	Yes	—	Yes
3	Yes	—	Yes	No ¹
4	Yes	—	—	Yes
5	—	Yes	Yes	No ¹
6	—	Yes	—	No ¹
7	—	—	Yes	No ¹
8	—	—	—	No ¹

¹ Not allowed per database design.

Dates will be imputed initially toward a specified target date for imputable scenarios 2, 4, and 8, and adjusted against the latest reasonable dates. The initial imputed date is determined by the following algorithm:

Table 6–3 Initial Imputed Date Algorithm

Available Year (YYYY)	Available Month (MM)			
	Missing	< Target Month	= Target Month	> Target Month
Missing	Target Date	—		
< Target Year	YYYY-12-31	YYYY-MM-LD		
= Target Year	Target Date	YYYY-MM-LD	Target Date	YYYY-MM-01
> Target Year	YYYY-01-01	YYYY-MM-01		

LD = last day of the month; MM = available start date month; YYYY = available start date year.

6.5.2.1. Missing/Incomplete AE and Medication Start Date

Imputation of dates with missing day and/or month is required for the start date of an AE and medication. If adequate information is available, no imputation is needed. AE and medication start dates with missing day or month will be imputed as following:

- If day and month are missing but year is available, then the imputed day and month will be 01 Jan or the operation date if they have the same year, whichever is later

CONFIDENTIAL

Draft Statistical Analysis Plan v2.0

XEN-45 Gel Stent

- If day is missing but the month and year are available, then the imputed day will be the first day of the month or the randomized operation date if they have the same month and year, whichever is later.

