5.3.1. Definition of Primary Endpoint

The primary effectiveness endpoint is the proportion of responders meeting all criteria below:

- Achieving $\geq 20\%$ mean IOP reduction from baseline at Month 12
- No increase in number of topical IOP-lowering medications at Month 12 compared to the baseline
- No clinical hypotony
- No loss of vision to count fingers or worse
- No secondary glaucoma surgical intervention.

The IOP will be assessed at all study visits by standard Goldmann Applanation Tonometry. For each IOP assessment, two consecutive measurements will be taken for each eye. If these 2 measurements differ by > 1 mm Hg, a third measurement will be performed for the given eye. The IOP value for a given eye will be the average of all measurements, which will be obtained from the eCRF, and the percent change from baseline at Month 12 will be computed as

$$\text{Percent change} = \frac{\text{Month 12 IOP} - \text{Baseline IOP}}{\text{Baseline IOP}} \times 100$$

The subject having the computed value of ≤ -20 will be considered achieving $\geq 20\%$ mean IOP reduction from baseline at Month 12.

The usage of topical IOP-lowering medication will be collected in the concomitant medication page. The IOP-lowering medication that were started before the Month 12 visit and stopped on or after the Month 12 visit or recorded as ongoing will be considered as the medication taken at Month 12. The partial start and stop dates of the medication will be imputed based on missing dates imputation rules specified in Appendix 3.

The clinical hypotony is defined as vision reduction (2 lines or more) related to macular changes consistent with hypotony maculopathy (macular folds), optic disc edema, and/or serous choroidal detachments because of low IOP. The following steps provide the identification of a patient with clinical hypotony. A patient at any time point with the following conditions:

- 1- filter any eyes with IOP of 6 mmHg or less, from this list...
- 2- Filter any eyes with VA reduction 2 lines or more compare to baseline, from the eyes left (and this is where it becomes more clinical and difficult, but the n should not be too high at this point)...
- 3- Filter any eyes that reported on the "OPHTHALMOSCOPY CRF" abnormal macula or periphery; AND any eyes that reported any of these AE:
 - Anterior chamber shallow with peripheral irido-corneal touch
 - Anterior chamber flat with irido-corneal touch

CONFIDENTIAL

Draft Statistical Analysis Plan v2.0

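### A start-date rule shared by adverse events and medications can relabel some preoperative glaucoma drops as starting at surgery, and can fail a true responder if the baseline drop count is built from those dates

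*SAP*

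**What the plan says.** SAP 6.5.2.1 covers both kinds of record: "AE and medication start dates with missing day or month will be imputed as following". Two rules follow.

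- Day and month missing: "then the imputed day and month will be 01 Jan or the operation date if they have the same year, whichever is later".
- Day missing only: "the imputed day will be the first day of the month or the randomized operation date if they have the same month and year", again whichever is later.

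The section also says "If adequate information is available, no imputation is needed", but does not define what is adequate.

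SAP 5.3.1 links these dates to the primary endpoint. One responder criterion is "No increase in number of topical IOP-lowering medications at Month 12 compared to the baseline". The only data source named is the medication log: "The usage of topical IOP-lowering medication will be collected in the concomitant medication page". A drug counts at Month 12 if it started before that visit and had not stopped by then. The next sentence reads "The partial start and stop dates of the medication will be imputed based on missing dates imputation rules specified in Appendix 3"; the rules themselves are in 6.5.2.

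SAP 5.1 places baseline before the study intervention, in general at Preoperative Visit 1. No section says how the baseline number of drops is derived. Inclusion criterion 6 in the protocol requires at least one topical IOP-lowering drug.

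**The concern.** Taking the later of two dates is cautious for adverse events, because doubtful events become treatment-emergent. For medications it works the other way. A glaucoma drop that the patient was already using is treated as new on the day of surgery. It is then missing from a date-derived baseline count but still present at Month 12, so an unchanged or reduced regimen can look like an increase.

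The criterion is one of five that an eye must meet to be a responder, so a single misclassified count changes the primary outcome for that eye. The rule has no exception for a drop reported at a preoperative visit. It also does not check an imputed start against a known earlier stop date, although protocol 8.4.5 allows drops to be stopped 1 to 4 weeks before surgery.

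**Working it through.** No figure in the plan depends on this rule, so there is none to reproduce. The check applies the rule to test dates, finds when the criterion flips, and then gives a scale.

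**Step 1. Apply the rule.** Illustrative dates: Visit 1 on 3 Sep 2019, operation on 16 Sep 2019, Month 12 visit on 15 Sep 2020. Each case is one drop, truly started before Visit 1 and ongoing at Month 12. The baseline count is taken from the imputed dates as the drops started by Visit 1.

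| Start recorded as | Imputed start (6.5.2.1) | Baseline count | Month 12 count | Criterion |
|---|---|---|---|---|
| 2019 only (true start March) | 16 Sep 2019 | 0 | 1 | fails |
| Sep 2019 (true start 1 Sep) | 16 Sep 2019 | 0 | 1 | fails |
| Mar 2019 | 1 Mar 2019 | 1 | 1 | met |
| 2018 only | 1 Jan 2018 | 1 | 1 | met |

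In the first two rows the true counts are 1 and 1, so the eye should pass. A baseline of 0 is also impossible for an eligible eye.

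**Step 2. When does an eye flip?** Let b be the true baseline count, m the Month 12 count, and k the number of preoperative drops moved to the operation date. The derived baseline is b − k, and the eye fails if m > b − k. The smallest k that fails a true responder (m ≤ b) is b − m + 1.

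- m = b: one moved drop is enough.
- m = b − 1 (with m at least 1): two are needed.
- m = 0: k would have to be b + 1, more drops than exist, so the eye cannot fail this way.

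Moving a preoperative start to the operation date leaves m unchanged, because both dates precede Month 12. It can only lower the baseline count, so on this criterion the error runs from responder to failure.

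**Step 3. Scale.** SAP section 3 gives 68 XEN and 34 trabeculectomy completers. One eye is 1/68 = 1.5 points or 1/34 = 2.9 points.

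The documents give no frequency of partial dates. As an assumption, let a share q of true responders be flipped, with a true rate of 70% in both arms (the SAP's planning value for trabeculectomy, applied here to XEN as well). Take the extreme case in which only XEN eyes flip, so p1 = 0.70(1 − q). The lower 95% limit is

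p1 − 0.70 − 1.96 × √[p1(1 − p1)/68 + 0.70 × 0.30/34].

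| q | p1 | XEN responders lost (of 47.6) | Lower limit |
|---|---|---|---|
| 0 | 0.700 | 0 | −18.9% |
| 1% | 0.693 | 0.5 | −19.6% |
| 2% | 0.686 | 1.0 | −20.3% |
| 5% | 0.665 | 2.4 | −22.6% |
| 10% | 0.630 | 4.8 | −26.2% |

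The margin in SAP section 2 is −24%.

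If both arms lose the same share, the difference stays at 0 and only the standard error grows. At q = 10% the limit is −1.96 × √[0.63 × 0.37 × (1/68 + 1/34)] = −19.9%.

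**Step 4. Table 6-3 beside 6.5.2.1.** The table's footnote describes start dates. Relative to its target date, an earlier year becomes 31 December and an earlier month becomes its last day; 6.5.2.1 gives 1 January and the first day. The target date is not defined. The text says "Dates will be imputed initially toward a specified target date for imputable scenarios 2, 4, and 8", yet Table 6-2 marks scenario 8 as not imputable. If the target is the operation date, the table agrees with 6.5.2.1 for a year-only start in the surgery year. The two differ on baseline status only in edge cases. One example is Visit 1 on 20 Dec 2019, surgery on 10 Jan 2020 and a start recorded as 2019: 1 Jan 2019 by 6.5.2.1, but 31 Dec 2019, after Visit 1, by the table.

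**The case against.** The strongest reply is that the SAP never says the baseline count is built from imputed dates. The date-based rule in 5.3.1 is written for Month 12 only, and the Month 12 count is unaffected. Other text points to a count taken at a visit: SAP 5.1 speaks of the last non-missing value before intervention, the schedule of assessments has a medication review at both preoperative visits, protocol 11.1.3 refers to the number of medications at screening, and SAP 6.3.3 lists a missing baseline medication count as a major deviation. If such a recorded count is used, the problem disappears. This stands, and it makes the harm conditional. It does not remove the point: the medication log is the only source that 5.3.1 names, and none of these hints is tied to the endpoint derivation.

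The adequate-information clause might also protect a drop documented at the qualifying visit, and an impossible baseline of 0 might be queried. But the clause is undefined, and a fall from 2 to 1 would look plausible and pass unnoticed.

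A reader might infer that every partial start in the surgery year is moved. It is not: a known month before the operation month stays preoperative. A reader might also infer that the Table 6-3 conflict drives the harm. It matters only in edge cases and is mainly a drafting fault.

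**Conclusion.** The rule is wrong as written for medications and should be changed. It reclassifies preoperative drops as starting at surgery in two situations: year-only starts in the surgery year, and day-missing starts in the operation month. If the baseline count is derived from these dates, an eye still on drops at Month 12 can wrongly fail the primary endpoint, and the error on this criterion has one direction.

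The size is unknown, because the documents do not say how many start dates are partial. The figures of 1.5 and 2.9 points are per affected eye, and the shares tabulated above are assumptions. It would be tempting to conclude that the rule biases the comparison against XEN, or could by itself cost the non-inferiority claim. The documents do not support that. The rule applies to both arms; a loss in XEN alone is an extreme case; and an equal loss of 10% in both arms moves the illustrative limit only from −18.9% to −19.9%. A difference between arms would need different drop use at Month 12 or different date quality, and neither is given.

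**What to change.** - Confine the later-of-two-dates rule in 6.5.2.1 to adverse events.
- State in 5.3.1 that the baseline medication count is the number of IOP-lowering drops recorded as in use at a named baseline visit.
- For IOP-lowering medications, impute a partial start to the earliest date consistent with the known parts, unless the drug is recorded as started after surgery. Never place a start after a visit at which the drug was reported, or after its known stop date.
- As a tidy-up, reconcile Table 6-3 with 6.5.2.1 or drop it for start dates, define its target date if it is kept, settle scenario 8, and correct the Appendix 3 cross-reference in 5.3.1.

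The cost is SAP wording and derivation code. No new data are needed provided that the medication reviews scheduled before surgery were recorded; this should be confirmed against the eCRF before the wording is settled.
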